**TITLE:**

Computerized Substance Use and Depression Screening and Behavioral Treatment in HIV Primary Care

NCT NUMBER:

NCT03217058

VERSION DATE:

October 5, 2022

Research Question: What are the key barriers to implementation, factors associated with effectiveness, and cost of tablet-based screening for the continuum of SUD severity and depression, followed by BHS-delivered interventions for those who screen positive.

Aim 1. To evaluate the implementation of computerized SUD and depression screening and BHS-delivered intervention in HIV primary care.

Hypothesis 1: SUD and depression screening rates and BHS-delivered intervention will be higher in the intervention phase compared with the observation phase and will be maintained long-term.

Hypothesis 2: Greater HIV severity and younger age will increase screening rates for SUD and depression.

Hypothesis 3: More BHS-delivered intervention will occur with higher HIV, SUD and/or depression severity.

Aim 2. To examine the effectiveness of computerized screening and BHS-delivered intervention in HIV primary care among patients with moderate or high SUD risk or depression severity.

Hypothesis 1: SUD and/or psychiatry specialty care treatment initiation and antidepressant prescription use will be greater in the intervention phase compared with the observation phase.

Hypothesis 2: HIV outcomes, including ART adherence, HIV RNA control, VACS index score, and retention in HIV care will be improved in the intervention phase compared with observation phase.

Hypothesis 3: SUD and depression symptoms will decrease after implementation of the intervention.

Aim 3. To determine implementation costs and cost-effectiveness of screening and BHS-delivered intervention.

We will measure the cost per patient screened, and among those screening positive, the cost per patient initiating BHS-delivered intervention. We will also evaluate the cost-effectiveness of the intervention for achieving improvements in each HIV, SUD and depression outcome.

Aim 4: Perform key informant interviews to evaluate provider- and clinic-level implementation barriers and facilitators to computerized screening and BHS-delivered intervention.

Semi-structured interviews for selected providers and clinic staff, including qualitative and quantitative components, will be performed in each clinic.

Study Design

Description of Study Phases

Phase 1: Data only

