The study team will assist the clinics in programming computerized screening measures, contacting patients via secure message on behalf of clinicians, and training a BHS to deliver evidence-based interventions. Patients will be informed that completing the questionnaire is part of Kaiser Permanente research and completion is voluntary. This information is included in both the secure message language (for those who have KP.org) as well as in the questionnaire instructions that are displayed on the tablet or computer device during administration (see language in "Secure Message" document and "TAPS/AOQ Questionnaire").

Prior to and during routine annual HIV clinic visits, HIV patients will be asked via secure message to complete the questionnaire in KP.org. Patients who do not complete the questionnaire prior to registration in the clinic will be instructed by a receptionist to complete it on a tablet in the waiting room. Clinicians will also have an opportunity to administer the questionnaire on an as needed basis (e.g. if the tablet is unavailable) via suspended hyperspace during the clinical visit. Clinic staff will be trained by Drs. [name] and [name] on questionnaire administration and interpretation. The results will be directly incorporated into the EHR and viewable by clinical staff including physicians and BHSs. Next, BHSs will review screening results and initiate MI- and CBT-based interventions as needed during the clinic visit and/or by phone. The study will employ a stepped wedge design, with implementation and effectiveness outcomes in the intervention phase compared with outcomes in the 12-month observational phase (i.e., usual care in 12 months prior to implementation). Rollout of the intervention will occur sequentially at the 3 clinics over two years (including 6-months overlap between clinics), allowing for refinement of the intervention accommodating the unique implementation challenges at each site.

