KPNC EHR. The EHR databases links information using unique member identifiers from multiple data sources including demographics, membership, ambulatory, inpatient, laboratory and prescription data. Unit costs of services obtained for each patient encounter and service are also available and can be calculated by member over time, or aggregated to physician or facility level. Vital status is captured comprehensively from member proxy reporting, deaths during a KP hospitalization, regional cancer registry vital status, quarterly Social Security Administration vital status files and death certificates. Additional detail on all EHR data sources is provided in KPNC Resources. After implementation of the intervention, results of KP.org-, tablet-, and suspended hyperspace-based SUD and depression screening during routine primary care visits will be added to the EHR. **HIV registry.** The HIV registry includes all HIV patients since the early 1980s, with HIV-infection confirmed by chart review. It maintains up-to-date lists of all HIV patients, HIV transmission risk factors, dates of known HIV infection, AIDS diagnoses, and complete HIV-related lab and pharmacy data. A total of 8,186 HIV patients are current KPNC members, including 4,600 (56% of all KPNC HIV patients) from the three study clinics.

Study Measures. We will include relevant patient demographic factors in all analyses, including age, sex, race/ethnicity, and HIV risk group. Evaluating these demographics in the context of an insured population allow for the evaluation of potential disparities in screening and treatment rates, independent of differences in access to care. Other study measures for each study Aim are described below.

Aim 1 measures (implementation)

- **SUD and depression screening** during the observational phase will include EHR-based provider-documented screening for SUDs and depression. Intervention phase screening will include provider-documented screening and KP.org-, tablet-, and suspended hyperspace-based screens, also in the EHR.
- **BHS-delivered intervention** during the observational and intervention phases will be defined as one or more in-person or phone visits with a BHS. We will also measure the number of phone and in-person visits.

Aim 2 measures (effectiveness)

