- **SUD and depression treatment initiation.** Patients scoring in the high SUD risk level on the TAPS or moderate to severe depression on the PHQ-9 will be encouraged to initiate specialty SUD or psychiatry treatment, and the BHS will use MI to help enhance motivation to initiate care. We will analyze SUD and depression treatment initiation rates using electronic administrative data; that is, whether the patient attended at least one in-person or phone visit with a BHS and/or in SUD or psychiatry treatment.
- **Antidepressant prescription rates.** Any prescription for antidepressants, including standard medications based on best practices guidelines in the treatment of depression.^{211,230}
- **Antiretroviral (ART) medication adherence.** ART adherence will be defined using the Medication Possession Ratio (MPR)^{234,235} for each ART prescribed.²³⁶ MPR is calculated using a numerator of days' supply dispensed from first fill to end of the interval (i.e., 12 months), and a denominator of total days between first fill to end of the interval, with values ranging from 0% to 100%. Mean refill adherence will be calculated across all individual ARTs dispensed in the interval²³⁷ distinguishing between true non-adherence or a change in ART (i.e., a new ART medication prescribed within 30 days) as in our previous work.^{238 179}
- **HIV RNA response.** HIV RNA control, defined as undetectable HIV RNA levels below 75 copies/ml.
- **Retention in care.** We will use the Institute of Medicine's encounter-based definition of retention, defined as ≥ 2 HIV primary care visits within a 12-month period, ≥ 90 days apart.¹⁵⁵
- **VACS index score.** The VACS score has been shown to correlate with mortality.¹⁸⁶ It incorporates 7 routinely collected clinical variables, including age, CD4, HIV RNA, hemoglobin, fibrosis index 4 (FIB-4), Hepatitis C, and

estimated glomerular filtration rate. The FIB-4 index incorporates age, platelets, and two liver function test results, including aspartate aminotransferase and alanine aminotransferase.

- **TAPS (SUD risk level) and PHQ-9 (Depression).** See section **C.6.b.**

Data Analysis

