Overview. The proposed study's primary aims are to examine the implementation and effectiveness and cost of computerized screening and BHS-delivered intervention. In context of the stepped wedge study design, HIV, SUD and depression outcomes will be compared between the intervention and observational phases. We will evaluate both short-term (i.e., within intervention phase) and long-term (i.e., within 1-2 years after initial intervention phase). As described in detail below, we will also employ two complementary study designs: 1) a repeated cross-section design with a different mix of individuals in each cluster (clinic) for examining implementation outcomes (e.g., Aim 1: screening rate) and 2) a cohort design for examining effectiveness in outcomes over time within the same individuals (e.g., Aim 2: retention in HIV care). Finally, we will evaluate implementation cost and cost-effectiveness, and perform qualitative interviews to assess provider- and clinic-level implementation barriers.

General Random Effects Model. Data analysis for both the cross-sectional and cohort approaches will use the random effects modeling framework which accounts for correlation between individuals within clusters and over time and is generalizable to non-normal distributions.¹¹ The general linear model is written as: $Y_{ijk} = m_{ij} + a_i + b_j + QX_{ij} + \epsilon_{ijk}$

where Y_{ijk} denotes the outcome for individual k in cluster i at time j . m_{ij} is the mean for cluster i at time j , a_i is the random effect for cluster i , β_j represent fixed effect corresponding to time j , and X_{ij} is the treatment mode in cluster i at time j . α_i and ϵ_{ijk} are independently distributed with appropriate distributions (e.g., logistic for binary outcomes, normal for continuous outcomes) and individual level covariates (e.g., gender, age, severity) to describe mean responses may be added to this model. The underlying distribution from the model can be linked to a linear predictor by appropriate transformations (e.g. binary outcome linearized using a logit link). These models may be estimated using SAS PROC MIXED or PROC NLMIXED for normal or non-normal distributions allowing for correlation between observations and variable cluster sizes.

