Aim 2. To examine the effectiveness of computerized screening and BHS-delivered intervention in HIV primary care among patients with moderate or high SUD risk or depression severity. We will first compare treatment initiation in specialty clinic for those with severe SUD or depression problems and anti-depression medication prescription rates, among all patients who screen positive (**Aim 2, Hypothesis 1**). The repeated cross-section analyses will be conducted using the random effects (mixed) model framework as above with the dependent variable (whether a patient received any prescription orders initiation with SUD specialty care or Psychiatry treatment for their SUD (depression) being dichotomous. Drawing from preliminary analyses, we will include all patient-level predictors (e.g. demographics such as age and gender, severity) that are likely to be related to these outcomes. These models will use logistic regression since the outcome is dichotomous. We will use the SAS® NL MIXED or similar procedure for analyses. Sample size permitting, we will also examine the use of Buprenorphine/Naloxone for the subset of HIV patients with opioid addiction.^{243,244}

We will also examine the longitudinal (cohort) effect of the intervention on clinical outcomes by comparing changes in HIV clinical parameters (**Aim 2, Hypothesis 2**) and SUD and depression severity (**Aim 2, Hypothesis 3**) for those who have return visits within the study observation period, adjusting for time between visits. We will examine changes in these values between the patient's initial screening and their subsequent visits using the random effects model described above. For example, we expect the coefficient of interest of the time x intervention variable to be positive, which would imply that BHS-delivered intervention results in greater increase in ART adherence.

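### The return-visit restriction and visit-gap adjustment for Aim 2 Hypothesis 2 also cover, as written, retention in care, an outcome made of visit count and spacing

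*Protocol*

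**What the plan says.** Four places in the protocol bear on this point.

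- **Aim 2, Hypothesis 2** expects that "HIV outcomes, including ART adherence, HIV RNA control, VACS index score, and retention in HIV care will be improved in the intervention phase" relative to the observation phase. Retention is one of four outcomes listed.
- **Study Measures, Aim 2 measures, Retention in care** defines the outcome as at least "2 HIV primary care visits within a 12-month period", with the visits at least 90 days apart. It does not say when the 12 months begin.
- **Data Analysis, Overview** assigns a cohort design to outcomes followed "within the same individuals (e.g., Aim 2: retention in HIV care". Retention is the named example. The same paragraph extends long-term evaluation to "within 1-2 years after initial intervention phase".
- **Data Analysis, Aim 2** gives a single cohort rule, tagged Hypotheses 2 and 3. Change is examined "for those who have return visits within the study observation period, adjusting for time between visits", from the initial screening to later visits. No outcome is exempted.

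The design description (Study Design, Phase 2, repeated in Study Procedures) is broader. It has "implementation and effectiveness outcomes in the intervention phase compared with outcomes in the 12-month observational phase" and sets no return-visit condition.

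**The concern.** A return-visit condition is reasonable where a second measurement is needed to see change, as with TAPS or PHQ-9. Retention is different, because coming back is the outcome itself. Restricting the analysis to patients who came back selects on that outcome. Adjusting for time between visits then holds fixed one of the two quantities from which it is built.

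At stake is the phase contrast in retention. The restriction can create a difference where there is none or hide one that exists, and the adjustment can remove part of an effect that works through visit spacing.

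**Working it through.** The protocol states no retention rate, return-visit rate, sample size or power for this analysis, so it has no figure to reproduce. The check is a reading of the text, followed by illustrations on assumed rates.

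**Step 1: does the rule reach retention?** The cohort rule is tagged Hypothesis 2; Hypothesis 2 lists retention; the Overview names retention as the cohort example. The rule's own worked example is ART adherence, which is computed from dispensing, so the rule is not confined to laboratory values. If retention fell outside it, the protocol would describe no cohort analysis for the outcome it uses to illustrate that design.

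**Step 2: the denominator.** Take the 12 months from the screening visit.

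- A patient with no later visit has one visit in the window, so is not retained, and is excluded.
- A patient who first returns after month 12 is also not retained. This patient stays in if the study observation period, which is not defined, exceeds 12 months.

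The restriction therefore removes some failures and may keep others.

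**Step 3: the adjustment.** With exactly two visits in the window, retention is 1 if the gap is at least 90 days and 0 otherwise. Among such patients with the same gap, everyone has the same outcome, so no phase difference is left to estimate. The protocol does not say how common these patients are, and this effect is not quantified here.

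**Step 4: illustration with the same individuals in both phases.** All inputs are assumed.

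- R0, R1: share retained in the observational and intervention phases, both 75% (true change 0)
- U: share alive and enrolled with no return visit in the study observation period
- r0: share of those retained in the observational phase
- q: share of those retained in the intervention window; 0 if the window starts at screening

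Among returners:

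- before = (R0 − U·r0)/(1 − U)
- after = (R1 − U·q)/(1 − U)
- distortion = (after − before) − (R1 − R0) = U·(R1 − R0 + r0 − q)/(1 − U)

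Count check with 1,000 patients, U = 5%, r0 = 50%, q = 0: 50 patients leave, 25 of them retained before and none after. Before: (750 − 25)/950 = 76.3%. After: 750/950 = 78.9%. The difference is 25/950 = 2.6 points.

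| U | q = 0, r0 = 30% | q = 0, r0 = 50% | q = 0, r0 = 75% | q = 70%, r0 = 50% |
|---|---|---|---|---|
| 2% | +0.6 | +1.0 | +1.5 | −0.4 |
| 5% | +1.6 | +2.6 | +3.9 | −1.1 |
| 10% | +3.3 | +5.6 | +8.3 | −2.2 |

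Entries are percentage points of false change. The last column represents a window tied to the calendar phase, in which some never-returners could still be retained.

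**Step 5: illustration with the restriction applied separately in each phase.** Let n be the share with no return visit and s the share of returners whose visits meet the 90-day spacing. Retention in all patients is (1 − n)·s; in returners it is s. With s = 85% and n falling from 20% to 10%, the full-cohort figure goes from 0.80 × 0.85 = 68.0% to 0.90 × 0.85 = 76.5%, a gain of 8.5 points. The restricted figure is 85% in both phases, a gain of 0. Here the rule hides a real improvement.

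**The case against.** The strongest reply is that the sentence was not written with retention in mind. It speaks of clinical parameters and of values that change from the screening visit to later visits. Retention is a 12-month status with no value at a single visit, so the rule cannot be applied to it literally, and the design description already gives a phase comparison without the condition. Much of this stands: the coverage is probably unintended. But the protocol still fixes an analysis set and an adjustment for Hypothesis 2 and exempts nothing.

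A second reply is that the window start, the observation period, and the handling of deaths and leavers belong in a statistical analysis plan. That is fair, and their absence is not the point. The point is a stated restriction and adjustment that do not suit this outcome.

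A third reply concerns the figures, and it too is largely right. Every input is assumed. The 70% column fits the workflow poorly: unscreened patients are flagged at appointments, so someone with two qualifying visits in the intervention phase would usually be screened at the first and counted as a returner at the second. The calculation is a simple before-after difference among returners, whereas the protocol's coefficient of interest is time by intervention, which was not modelled.

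A reader might infer that the plan is tilted towards a favourable retention result. The documents do not support that. The lean towards a gain needs a window starting at screening and the same patients in both phases; under other readings an effect is hidden or the lean reverses. Nor do they show that Hypothesis 2 as a whole is compromised. For ART adherence, HIV RNA and VACS the condition raises ordinary selection on follow-up, which is a separate matter.

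**Conclusion.** The point holds for retention in care, one of four Hypothesis 2 outcomes. As written, the cohort rule conditions the analysis of a visit-based outcome on having visits and adjusts for their spacing. That never-returners are failures removed from the denominator follows from the definition alone, provided the 12 months run from the screening visit.

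Size and direction cannot be determined from the protocol. The illustrations run from a false gain of 0.6 to 8.3 points (window from screening), through a false loss of 0.4 to 2.2 points (calendar-phase window, weakly supported), to complete masking of an 8.5-point gain (restriction applied per phase). They show what the rule can do and do not estimate what it will do. The wording should be corrected before the retention analysis is run.

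**What to change.** For retention only, in Data Analysis, Aim 2:

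- Remove the return-visit condition and the adjustment for time between visits.
- Analyse retention as yes/no over a fixed 12-month period in each phase, in line with the design description's phase comparison.
- Include all patients in the Aim 2 at-risk cohort, the same individuals in both phases as the Overview states.
- Count patients who are alive and enrolled but have no qualifying second visit as not retained.

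Leave the rule unchanged for the other Hypothesis 2 and 3 outcomes.

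No new data collection is needed. Under Data Sources, KPNC EHR, "Vital status is captured comprehensively from member proxy reporting" and other sources, and the EHR links "multiple data sources including demographics, membership, ambulatory, inpatient, laboratory and prescription data", so visits, death and enrolment can all be established.

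There are two costs. Absolute retention rates will look lower, because patients who do not return now count. And because TAPS-based risk status is known only from the intervention phase, the protocol must state how the observational-phase window is anchored for these patients; that rule has to be written, as the current text does not supply it.

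### The cohort analysis of ART adherence is limited to patients who return, although MPR comes from pharmacy fills and needs no visit, so selection on returning can distort the effect

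*Protocol*

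**What the plan says.** Aim 2, Hypothesis 2 at the front of the Protocol states that "HIV outcomes, including ART adherence, HIV RNA control, VACS index score, and retention in HIV care will be improved in the intervention phase" relative to the observation phase. Adherence, HIV RNA and retention therefore sit in one hypothesis.

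Data Analysis, Aim 2 describes the cohort analysis as "comparing changes in HIV clinical parameters" for Hypothesis 2, together with substance use and depression severity for Hypothesis 3, "for those who have return visits within the study observation period, adjusting for time between visits". It continues: "We will examine changes in these values between the patient's initial screening and their subsequent visits using the random effects model described above". The coefficient of interest is time by intervention. For adherence it is expected to be positive, "which would imply that BHS-delivered intervention results in greater increase in ART adherence".

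Aim 2 measures (effectiveness) defines MPR as days' supply dispensed, from first fill to the end of a 12-month interval, over the days in that span. HIV RNA control is a laboratory value below 75 copies/ml. Retention requires at least two "HIV primary care visits within a 12-month period", at least 90 days apart. Data Sources says that the HIV registry maintains "complete HIV-related lab and pharmacy data" and counts 4,600 current patients at the three study clinics.

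**The concern.** One rule is applied to two kinds of outcome. TAPS and PHQ-9 scores exist only if a patient completes another questionnaire, so restricting those analyses to returning patients is understandable. MPR is different: a patient who never comes back still has a fill history. Excluding that patient discards data already held and conditions the analysis on an event after exposure that the programme is meant to influence.

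Two things are at stake. First, the patients analysed may differ between phases for reasons that the intervention itself causes. Second, a benefit that works by keeping people in care, and hence on treatment, may not show in an analysis of returning patients only. The one adjustment in the sentence, for time between visits, cannot repair this, because excluded patients contribute nothing to the model. No other section gives an adherence analysis that includes them.

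**Working it through.** The Protocol gives no return rate, no adherence by return status and no design effect for this analysis, so there is no planned figure to reproduce. The only adherence figures are in the illustration under Aim 3, a rise in mean adherence from 85% to 90%, or 5 points. It serves here only as a yardstick.

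**Assumed inputs (none is in the document).** r0 and r1 are the shares returning in the observation and intervention phases. A is mean MPR in patients who return in either phase, and m is mean MPR in patients who return only under the intervention. The formulas take the return condition to be applied separately in each phase.

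**Step 1: phase mean levels, no true effect on adherence.**

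Shift = [r0·A + (r1 − r0)·m]/r1 − A = −(r1 − r0)/r1 × (A − m), with A = 88.

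| r0 | r1 | m | Calculation | Shift (points) |
|---|---|---|---|---|
| 0.85 | 0.88 | 70 | (74.8 + 2.1)/0.88 − 88 | −0.61 |
| 0.80 | 0.85 | 70 | (70.4 + 3.5)/0.85 − 88 | −1.06 |
| 0.80 | 0.85 | 60 | (70.4 + 3.0)/0.85 − 88 | −1.65 |
| 0.80 | 0.90 | 60 | (70.4 + 6.0)/0.90 − 88 | −3.11 |

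**Step 2: within-patient change, which is what the Protocol tests.** Let d be the change in MPR over time in patients who return only under the intervention, minus the change in those who return in either phase. With no true effect:

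Shift in the change contrast = (r1 − r0)/r1 × d.

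If the newly returning patients are lower by a constant amount at both times, d = 0 and all four shifts in Step 1 become 0. With assumed values of d:

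| Return, r0 to r1 | d = −10 | d = −20 | d = −40 |
|---|---|---|---|
| 80% to 80% | 0 | 0 | 0 |
| 80% to 85% | −0.6 | −1.2 | −2.4 |
| 80% to 90% | −1.1 | −2.2 | −4.4 |
| 70% to 85% | −1.8 | −3.5 | −7.1 |

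A positive d gives the same sizes with the opposite sign.

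**Step 3: a benefit that acts only through retention.** Suppose that patients kept in care by the intervention avoid a fall of g points and then change as other returning patients do. The effect in all patients is (r1 − r0) × g:

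- 0.05 × 20 = 1.0 point
- 0.10 × 20 = 2.0 points
- 0.10 × 40 = 4.0 points
- 0.15 × 40 = 6.0 points

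The contrast among returning patients is 0 in each case, because the patients who fell are outside the observation-phase set.

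**The case against.** The strongest objection concerns size. A reader might infer from Step 1 that the adherence effect is biased toward no effect or harm by 0.6 to 3.1 points. The document does not support that. Those figures compare levels, whereas the Protocol tests change within patients, where a constant gap in level largely cancels. This stands: bias needs a gap in change, and the Protocol gives no information on one.

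Second, the Data Analysis overview describes a cohort of the same individuals over time, and the return condition refers to the study observation period, not to each phase. If one set serves both phases, the shift in composition in Steps 1 and 2 does not arise. The text allows either reading. The single-set reading still drops patients who do not come back, and any fall in their adherence goes with them, which could favour the intervention. This is a further reason not to claim a direction.

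Third, a return visit is not the retention outcome, which needs two visits at least 90 days apart within 12 months. Retention could improve with little change in the share who ever return. This stands too: the two are related, not identical.

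Fourth, a reader might infer that analysing everyone removes all bias. It does not. An HIV RNA result requires a blood draw, so complete laboratory records do not mean a result for every patient. MPR runs from a first fill and is undefined for a patient with none in the interval. The point is therefore strongest for adherence and weaker for HIV RNA.

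Fifth, analysis sets are often left to the SAP, which is not at hand. Here, however, the Protocol does not leave the set open. It states a restriction and uses adherence as the example.

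**Conclusion.** The point holds as an avoidable selection rule. The Protocol conditions the adherence analysis on an event after exposure, related to an outcome in the same hypothesis, although MPR can be computed without a visit from fills already held.

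The effect can be biased if two conditions hold together: return differs by phase, and patients who return only because of the intervention differ in their change in adherence. If either fails, the shift in Step 2 is zero. Separately, a gain obtained by keeping patients in care can go unseen; under the assumptions of Step 3 that is 1 to 6 points against an illustrative 5. Every return rate and gap used is an assumption, so these figures show what is possible and do not estimate what will happen.

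The change should be made, because the restriction serves no purpose for MPR.

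**What to change.** For MPR, analyse all patients in Aim 2's target group, those at moderate or high risk on substance use or depression, identified at a phase-specific index date. Follow each over the fixed 12-month interval while a health-plan member, whether or not the patient returns, and state a rule for patients with no fill. Widening the set to every clinic patient would depart from the population that Aim 2 names.

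Treat HIV RNA the same way, with a stated rule for no test, and acknowledge that some selection remains because a result needs a blood draw. Keep the return-visit restriction only for TAPS and PHQ-9, and report the proportion returning by phase.

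The cost is wording and extra extraction from records already held. The downside is small: the rules for no fill and no test are not in the Protocol now and must be written, as must the way the target group is identified in the observation phase, before TAPS is administered.
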